For analysis of efficacy endpoints, analysis of covariance (ANCOVA) or longitudinal models will model the observed value or change from baseline of each endpoint as the dependent variable with the baseline measurement of the corresponding endpoint as a covariate and treatment group as a main effect. Longitudinal models will include a covariate for visit as well as an interaction term for visit and treatment.

Subgroups

Not applicable.

Multiplicity

Time-matched longitudinal models adjusting for baseline and including a random effect for center will be used to test time-specific superiority comparisons as well as the overall superiority hypothesis using 95% confidence intervals. To claim study success for the primary endpoint based on the model, the two-sided 95% confidence interval estimates of the treatment differences in mean IOP between VVN539 and vehicle must exclude zero for all 9 time points (8AM, 10AM, and 4PM at Visits 4, 5, and 6). No adjustment to the individual confidence intervals is required since all criteria need to be met to claim superiority.

Comparisons will be made first between VVN539, 0.04% versus vehicle. If the treatment differences for all 9 time points are statistically significant, testing will proceed to VVN539, 0.02% versus vehicle.

Missing Data and Outliers

Every attempt will be made to capture all study data. The primary analysis will be analyzed using observed data assuming missing at random (MAR) using a longitudinal model (mixed model repeated measures, MMRM). Sensitivity analyses of the primary endpoint will be performed utilizing time-matched last observation carried forward (LOCF) of the last available IOP measurement.

Safety analyses will use observed data only.

Visit Windows

The nominal visits listed in the CRF will be used in the summaries. In general, unscheduled visits will not be summarized in tables unless otherwise noted.

Missing Dates

Missing dates that occur for prior or concomitant medications or adverse events will be queried for a date. If no date is obtained, the following imputation rules will apply:

- For start dates, if the given year (or year-month) is the same as study drug administration, the start date will be imputed as study drug administration date; otherwise, missing month-day (or day) will be imputed as '01-01' (or '01').

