- For stop dates, missing months will be imputed as '12' and missing days will be imputed as the last day of the month. If this creates a date after discontinuation/completion, the date of discontinuation/completion will be used.

Imputed dates will only be used to classify events or medications, such as occurring before or after the start of treatment. Imputed dates will only be used in tables. Listings will display the collected date data.

Interim Analysis

There is no unmasked efficacy or futility interim analysis for this study.

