9.7.1.3.3. Prior and Concomitant Medications

Prior and concomitant medications will be coded using the World Health Organization Drug Dictionary (WHODrug) (Version 2021-09, Lagerlund et al., 2020) for anatomical therapeutic chemical (ATC) classification and preferred drug name.

The frequency and percentage of subjects with coded medications will be summarized by treatment group using the Safety Analysis Set. A subject who used multiple medications will be counted only once for each ATC and preferred drug name. Therapeutic Subgroup is sorted alphabetically, and preferred term is sorted by descending frequency overall within each Level 3 term according to:

1. Descending frequency within VVN539, 0.04%;
2. Descending frequency within VVN539, 0.02%;
3. Descending frequency within Vehicle;
4. PT in alphabetical order.

Prior and concomitant medications will be summarized separately. Ocular medications are defined as those medications for which an eye has been specified (OD, OS, or OU). Ocular and non-ocular medications will be summarized separately. Ocular medications will be summarized separately for study eye, non-study eye, and either eye.

Prior medications are defined as any medications that started and stopped prior to the date of first dose of double-masked study drug. Concomitant medications are defined as any medications that (1) start prior to the date of first dose of double-masked study drug and stop or are ongoing at or after the date of first dose of double-masked study drug; or (2) start at or after the date of first dose of double-masked study drug. Medications started after Visit 6 or withdrawal from the study are not considered concomitant.

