9.7.1.6.1. Adverse Events

AEs are coded using MedDRA Version 24.1. Treatment-emergent adverse events (TEAE) are defined as events that start on or after the date of first dose of double-masked study drug up to and including the last dose of double-masked study medication. Ocular AEs are defined as those events for which an eye has been specified (OD, OS, or OU).

Ocular and non-ocular AEs will be summarized separately. Ocular AEs will be presented by study eye and non-study eye and overall (OU) if an event occurs in either eye.

In all summaries of AEs, percentages are calculated based on the number of subjects in each treatment group of the Safety Analysis Set.

Overall summaries of AEs by treatment will include:

- the number of AEs and SAEs reported;
- the number and percentage of subjects who experienced any AE;
- the number and percentage of subjects who experienced any serious adverse event (SAE) and the reason for seriousness;
- the number and percentage of subjects with any AE by worst severity and worst relationship.

The overall summaries of TEAEs will also include:

- the number and percentage of subjects with any TEAEs leading to discontinuation of double-masked study drug;
- the number and percentage of subjects with any TEAEs leading to study termination.

Summaries of the frequency and percentage of subjects with AEs by SOC and preferred term by treatment group will include:

- All AEs by SOC and preferred term;
- All AEs by SOC, preferred term, and maximum severity;
- All AEs by SOC, preferred term, and maximum relationship.

System organ class (SOC) will be sorted alphabetically, and preferred term (PT) within each SOC will be sorted by overall descending order of frequency according to the following rules in order:

1. Descending frequency within VVN539, 0.04%
2. Descending frequency within VVN539, 0.02%
3. Descending frequency within Vehicle;
4. PT in alphabetical order.

Subjects are counted only once for each SOC and PT. In summaries of maximum severity and maximum relationship, subjects with multiple occurrences of events will only be counted once at the maximum severity/relationship per SOC and PT.

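### The SAP's rule for partial start dates ignores a known stop date, so a medication or event that ended before first dose can be classed as concomitant or treatment-emergent (minor)

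*SAP*

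**What the plan says.** SAP 9.7.1, Missing Dates, covers medications and adverse events together. The first step is a query: "Missing dates that occur for prior or concomitant medications or adverse events will be queried for a date". If no date is obtained, a start date known only to the year or year-month is handled in one of two ways. Where the known part matches dosing, "if the given year (or year-month) is the same as study drug administration, the start date will be imputed as study drug administration date". Otherwise it goes to the first day of the known year or month.

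The only cap in these rules is on imputed stop dates: "If this creates a date after discontinuation/completion, the date of discontinuation/completion will be used". Nothing requires an imputed start to fall on or before the stop.

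The purpose of the imputation is stated: "Imputed dates will only be used to classify events or medications, such as occurring before or after the start of treatment". The SAP adds that imputed dates are for tables and that listings show the dates as collected.

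Three definitions then use the result:

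- SAP 9.7.1.3.3: "Prior medications are defined as any medications that started and stopped prior to the date of first dose of double-masked study drug".
- The second limb of the concomitant definition in the same section takes in any medication that "start at or after the date of first dose of double-masked study drug", with no condition on its stop date.
- SAP 9.7.1.6.1 defines treatment-emergent events as "events that start on or after the date of first dose of double-masked study drug", up to the last dose. The event's end date plays no part.

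**The concern.** Moving an uncertain start to first dose is a usual conservative choice when the timing really is unknown. Here the recorded stop date can settle the timing, and the rule overrides it with an impossible sequence in which the start follows the end.

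The plan collects the kind of record to which this can happen. Medications are recorded from 2 months before Visit 1 (SAP 9.5.1.2.3). Pressure-lowering drugs are washed out before Visit 2 (protocol 7.1.1). Adverse events are recorded from consent (SAP 9.5.1.4.1), with screening as early as Day -35 and first dose on Day 1.

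Two descriptive outputs are at stake. A washed-out pressure-lowering drug could be counted among concomitant ocular medications, although such drugs are barred on study except as rescue. An event that resolved before any dose could be counted as treatment-emergent in a first-in-human trial.

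**Working it through.** The plan gives no figure on this point, so there is none to reproduce. The check applies the rules literally to example records. Study drug administration is read as the first dose. The dates are assumed for illustration: first dose 20 Sep 2022, last dose 10 Oct 2022.

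**Step 1: the rules as written.**

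| Record | Recorded start | Recorded stop | Imputed start | Classification |
|---|---|---|---|---|
| Drug a | 2022 | 18 Aug 2022 | 20 Sep 2022 | Concomitant |
| Drug b | Sep 2022 | 13 Sep 2022 | 20 Sep 2022 | Concomitant |
| Event c | Sep 2022, or 2022 only | 12 Sep 2022 | 20 Sep 2022 | Treatment-emergent |
| Drug d | 2021 | 18 Aug 2022 | 1 Jan 2021 | Prior |
| Drug e | Jun 2022 | 18 Aug 2022 | 1 Jun 2022 | Prior |
| Event f | Aug 2022 | 12 Sep 2022 | 1 Aug 2022 | Not treatment-emergent |

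Records a to c are wrong. The imputed start falls after the recorded stop by 33 days (a: 13 days left in August + 20), 7 days (b: 20 - 13) and 8 days (c: 20 - 12). Records d to f are right.

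**Step 2: the same records with the imputed start no later than the known stop.** Drugs a and b become prior and event c becomes not treatment-emergent. Records d to f do not change.

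**Step 3: which pressure-lowering drugs can be caught.** Protocol 4.1 asks treated subjects for a stable regimen for 30 days before Visit 1. The shortest washout is 5 days before Visit 2, and first dose is the day after Visit 2. A qualifying drug therefore began at least 30 + 5 + 1 = 36 days before first dose. No month has more than 31 days, so its start cannot share a calendar month with first dose. The year-month branch cannot catch it, and only a year-only start in the dosing year can. Drug b is thus not a stable pre-study pressure-lowering drug. It stands for other short-course medications, or for a bridging drug under protocol 7.1.1, whose start the site should know.

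The synopsis omits the 30 days. Without them, the washout alone sets the limit:

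- For a 4-week class the stop is at least 28 + 1 = 29 days before first dose. Stop and dose then share a month on only 18 of 365 dosing days: days 30 and 31 of the seven 31-day months (14) plus day 30 of the four 30-day months (4).
- For a 5-day class the stop is at least 6 days before, which gives 365 - 12 × 6 = 293 of 365.

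**Step 4: size per record.** With 20 subjects per arm, one misclassified subject is 1/20 = 5 percentage points of that arm.

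**The case against.** The strongest reply is that the rule seldom applies and does little when it does.

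- Dates are queried first.
- Drugs begun in an earlier year or a known earlier month are classed correctly.
- The medication tables give counts by class and drug name and show no start dates. The listing would show the true stop.
- On-treatment use of other pressure-lowering drugs is followed elsewhere: rescue is annotated in the eCRF (protocol 5.5.1), and SAP 9.7.1.2 tabulates withdrawals for elevated IOP with rescue and major protocol deviations.
- The system organ class and preferred term tables in SAP 9.7.1.6.1 cover all adverse events. The items added for treatment-emergent events concern drug discontinuation and study termination, which an event resolved before dosing is unlikely to enter.
- Any error over-counts events, in line with the SAP's other cautious conventions, such as showing missing severity as severe.

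All of this stands as a limit on frequency and consequence. It does not make the classification right: for a record that meets the conditions, the stop date is known and the rule contradicts it.

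A reader might infer more: that most previously treated subjects would have a washed-out drug shown as concomitant, or that several would appear to have started a barred drug on the day of first dose. The documents do not support either. A count would need the number of previously treated subjects and the share whose start stays year-only, in the dosing year, after query. Neither is given, and the true number could be zero. Nor would any table show a start on the first-dose date.

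**Conclusion.** The point holds as a minor defect. The rule misclassifies every record that meets all three conditions: start still partial after query, known year or year-month equal to that of first dose, and a stop date showing an end before first dose. No other part of the protocol or SAP corrects it.

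The effect is limited to the prior and concomitant medication tables, the treatment-emergent summaries, and any listing selected by treatment-emergent status. Collected dates remain visible in listings. No IOP estimate, confidence interval or success criterion depends on the rule.

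The conclusion rests on a literal reading of the SAP, with study drug administration taken as first dose. Restricting the pressure-lowering drugs to year-only starts also rests on the 30-day stable-regimen wording of protocol 4.1 rather than the synopsis.

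**What to change.** Add to the start-date rule in SAP 9.7.1, Missing Dates:

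> If a complete or partial stop date shows that the medication or event ended before the first dose, it is classified as prior (or not treatment-emergent), and an imputed start date may not be later than the stop date.

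Keep the existing rule where the stop date is on or after first dose, ongoing or unknown. A partial stop that could fall on either side of first dose, such as the dosing month with no day, does not show an earlier end and so stays under the existing rule.

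The cost is one sentence in the SAP and one programming condition. No new data are needed.

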9.7.1.1. Analysis Populations

9.7.1.1.1. Populations

The Full Analysis Set (FAS) consists of all subjects who were randomized. Subjects will be analyzed in the group to which they were randomized. This set will be used for the analysis of all efficacy endpoints as the primary analysis.

The Per Protocol (PP) Analysis Set will include all subjects who completed study-required treatment and who followed the protocol without significant deviations. The determination of significant protocol violations, including the use of prohibited medications, will be made prior to locking the final database and unmasking. Subjects will be analyzed in the group to which they were treated.

The Safety Analysis Set will include all subjects who took at least one dose of investigational product as indicated on the dosing record. Subjects will be analyzed in the group according to the treatment received. All safety variables will be analyzed using the Safety Analysis Set and only observed data will be included (i.e., missing data will remain missing for the safety analysis).

A listing of subjects excluded from the analysis sets will be provided.

9.7.1.1.2. Analysis Eyes

The study eye is defined as meeting all inclusion criteria and no exclusion criteria, and with the higher IOP at 8:00AM at Visit 2. Should both eyes have the same IOP and meet all inclusion criteria and no exclusion criteria, then the right eye will be the study eye.

Efficacy analyses will focus on the study eye only, though supportive analyses will also be presented by the non-study eye, irrespective of qualification. Ophthalmic safety analyses will be presented by the study eye and non-study eye.

9.7.1.2. Analysis of Subject Disposition

The number of subjects randomized at each site will be summarized by treatment group and overall.

Subjects' enrollment and disposition during the study will be summarized by treatment group and overall based on Randomized Subjects. The reasons for discontinuation will be displayed in the order as they appear on the eCRF.

Summary tables will include the following. The percentages will be calculated based on the number of subjects randomized (with reasons for discontinuation based on the number of subjects discontinued).

- Number of patients screened;
- Number and percentage of subjects randomized;
- Number and percentage of subjects randomized with any protocol deviation;
- Number and percentage of subjects treated;
- Number and percentage of subjects treated with any protocol deviation;
- Number and percentage of subjects treated who completed the study through Visit 6 (Day 21);
- Number and percentage of subjects treated who discontinued from the study;
- The reasons for study discontinuation;
- Number and percentage of subjects withdrawn from study drug due to elevated IOP and subsequent rescue treatment;
- Number and percentage of subjects attending each visit.

A listing of subjects who do not meet all inclusion criteria or meet exclusion criteria will be provided. A table of major protocol deviations will be presented using the FAS.

9.7.1.3. Analysis of Demographic and Baseline Characteristics

9.7.1.3.1. Demographics and Disease Characteristics

Demographic and baseline disease characteristics including age (years), age group (18-<45, \geq 45), sex, race, ethnicity, iris color, study eye (OD/OS), normality of nerve fiber layer thickness, baseline diurnal IOP of the study eye, and baseline IOP at 8:00 AM, 10:00 AM, and 4:00 PM will be summarized descriptively by treatment group and overall using the FAS, Per Protocol, and Safety Analysis Sets. For categorical parameters, the percentages will be calculated overall and based on the number of subjects in each treatment group based on non-missing observations.

Ocular baseline characteristics for central corneal thickness (average of three measurements), gonioscopy, and visual field will be summarized by study eye and non-study eye.

9.7.1.3.2. Medical History

Medical history will be coded using the Medical Dictionary for Regulatory Activities (MedDRA Version 24.1, Mozzicato, 2009). The frequency and percentage of subjects with any medical history will be summarized by treatment group using the FAS. System organ class (SOC) will be sorted alphabetically and preferred term (PT) within each SOC will be sorted by overall descending order of frequency according to the following rules in order:

1. Descending frequency within VVN539, 0.04%;
2. Descending frequency within VVN539, 0.02%;
3. Descending frequency within Vehicle;
4. PT in alphabetical order.

The medical history will include both the ocular and the general (non-ocular) history. Ocular medical history and general (non-ocular) medical history will be summarized separately. Ocular and non-ocular medical histories are identified according to which CRF the event is recorded. Ocular medical history will be summarized separately for study eye, non-study eye, and either eye.

9.7.1.3.3. Prior and Concomitant Medications

Prior and concomitant medications will be coded using the World Health Organization Drug Dictionary (WHODrug) (Version 2021-09, Lagerlund et al., 2020) for anatomical therapeutic chemical (ATC) classification and preferred drug name.

The frequency and percentage of subjects with coded medications will be summarized by treatment group using the Safety Analysis Set. A subject who used multiple medications will be counted only once for each ATC and preferred drug name. Therapeutic Subgroup is sorted alphabetically, and preferred term is sorted by descending frequency overall within each Level 3 term according to:

1. Descending frequency within VVN539, 0.04%;
2. Descending frequency within VVN539, 0.02%;
3. Descending frequency within Vehicle;
4. PT in alphabetical order.

Prior and concomitant medications will be summarized separately. Ocular medications are defined as those medications for which an eye has been specified (OD, OS, or OU). Ocular and non-ocular medications will be summarized separately. Ocular medications will be summarized separately for study eye, non-study eye, and either eye.

Prior medications are defined as any medications that started and stopped prior to the date of first dose of double-masked study drug. Concomitant medications are defined as any medications that (1) start prior to the date of first dose of double-masked study drug and stop or are ongoing at or after the date of first dose of double-masked study drug; or (2) start at or after the date of first dose of double-masked study drug. Medications started after Visit 6 or withdrawal from the study are not considered concomitant.

9.7.1.4. Analysis of Study Medication Adherence and Exposure

Treatment adherence and exposure will be assessed by the data from the Study Drug Administration and Treatment Adherence eCRFs and will be summarized by treatment group using the Safety Analysis Set.

Treatment adherence was assessed by 3 questions: Did subject return (clinic staff), and two subject reported measures: Did subject miss any doses, and if so, how many doses missed. Descriptive statistics will be presented for these measures by visit by treatment group.

Duration of exposure of double-masked study drug will be calculated as the total number of days from the first double-masked dose date to the last double-masked dose date plus 1 (one) regardless of temporary dose interruptions. Other dosing durations are calculated as follows:

- For q.d. morning dosing, duration of exposure is calculated as Visit 4 date - Visit 3 date + 1. If the date of last dose is between Visit 3 and Visit 4 date (inclusive), the Visit 4 date is replaced with the date of last dose.
- For q.d. evening dosing, duration of exposure will be calculated as Visit 5 date - Visit 4 date. If the date of last dose is between Visit 4 + 1 date and Visit 5 date (inclusive), the Visit 5 date is replaced with the date of last dose.
- For b.i.d. dosing, duration of exposure will be calculated as Visit 6 - Visit 5 date. If the date of last dose is between Visit 5 + 1 date and Visit 6 date (inclusive), the Visit 6 date is replaced with the date of last dose.

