5.5.1 Management of Elevated IOP During Treatment

Any subject who has an elevated IOP that the PI considers unsafe for the subject may be rescued and placed on appropriate alternate therapy. The choice of rescue medication is at the Investigator's discretion. Rescue medication should be entered into the eCRF with annotation indicating that the medication was used for rescue.

Rescued subjects will be considered as treatment failures, and the need for rescue therapy will not be considered an adverse event (AE). Rescued subjects will stop the investigational product and should not be withdrawn from the study.

The following guidance is provided to Investigators for rescue and the decision to rescue is at the discretion of the investigator's judgement:

- Ocular hypotensive medication (other than IP) is prohibited during study participation unless the subject is rescued.
- If the subject's IOP is > 36 mm HG, the Investigator may recheck the IOP within 3 day of the visit and rescue medication may be considered if the IOP remains elevated
- Rescued subjects should discontinue the investigational product.
- Rescued subjects should continue in the study for safety follow-up after receiving the rescue medication.

6 Study Discontinuation/Subject Withdrawal

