9.7.1.5.1. Primary Efficacy Analysis

Primary Estimands: The primary estimands are the treatment differences between VVN539 and vehicle at 8:00 AM, 10:00 AM, and 4:00 PM at each of Days 7, 14, and 21 in the study eye using the FAS. The primary estimands treat subjects as if they do not receive rescue therapy.

Target Population: Subjects with open-angle glaucoma or ocular hypertension that meet the study entry criteria.

Endpoint: Observed IOP measurements at each time point in the study eye.

Treatment Condition(s): Treatment condition is based on the randomized treatment group.

Population-level Summaries: The difference in the mean IOP at the nine time points of interest and their corresponding p-values and 95% confidence intervals.

Intercurrent Events and Strategies to Address Intercurrent Events

- Discontinuation of study therapy with continued participation in the study without receipt of rescue therapy
 - Treatment Policy – no imputation; use observed data
- Receipt of rescue therapy in the study eye
 - Hypothetical Approach – data for visits after the receipt of rescue therapy will be set to missing and will be analyzed assuming missing at random (MAR) using a longitudinal model (mixed model repeated measures, MMRM)
- Missing data without withdrawal or with withdrawal regardless of reason
 - Hypothetical Approach: visits that are missing data will be analyzed assuming MAR using MMRM

Time-matched longitudinal models adjusting for baseline and including a random effect for center will be used to test time-specific superiority comparisons as well as the overall superiority hypothesis using 95% confidence intervals. To claim study success for the primary endpoint based on the model, the two-sided 95% confidence interval estimates of the treatment differences in mean IOP between VVN539 and vehicle must exclude zero for all 9 time points (8AM, 10AM, and 4PM at Visits 4, 5, and 6). Comparisons will be made first between VVN539, 0.04% versus vehicle. If the treatment differences for all 9 time points are statistically significant, testing will proceed to VVN539, 0.02% versus vehicle.

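### The SAP's per-regimen exposure rule credits full evening or b.i.d. exposure to a subject who stopped the product before that regimen began but kept attending visits

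*SAP*

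**What the plan says.** SAP 9.7.1.4 (Analysis of Study Medication Adherence and Exposure) gives four durations, summarized by treatment group in the Safety Analysis Set.

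- **Total exposure** runs "from the first double-masked dose date to the last double-masked dose date plus 1 (one) regardless of temporary dose interruptions".
- **Morning:** "For q.d. morning dosing, duration of exposure is calculated as Visit 4 date - Visit 3 date + 1". The last-dose date replaces Visit 4 if it lies between Visits 3 and 4.
- **Evening:** "For q.d. evening dosing, duration of exposure will be calculated as Visit 5 date - Visit 4 date". The last-dose date replaces Visit 5 only if it lies between the day after Visit 4 and Visit 5.
- **B.i.d.:** "For b.i.d. dosing, duration of exposure will be calculated as Visit 6 - Visit 5 date". The replacement rule is: "If the date of last dose is between Visit 5 + 1 date and Visit 6 date (inclusive), the Visit 6 date is replaced" by the last-dose date.

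Two other places show that a subject may stop the product and still have later visit dates. Protocol 5.5.1 states: "Rescued subjects will stop the investigational product and should not be withdrawn from the study". SAP 9.7.1.5.1 lists among its intercurrent events: "Discontinuation of study therapy with continued participation in the study without receipt of rescue therapy".

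**The concern.** The replacement rule works only when the last dose falls inside the regimen's own window. If the last dose came before the window opened, the condition is false, nothing is replaced, and the default visit-to-visit interval stands. A subject who never took a b.i.d. dose but attended Visits 5 and 6 is then recorded with a full b.i.d. duration. The morning rule has no such gap, because a treated subject's last dose cannot precede the first dose at Visit 3.

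The same section cuts total exposure correctly at the last dose, so it can give two irreconcilable answers for one subject. At stake is the per-regimen exposure summary. In a first-in-human study that moves every subject from q.d. to b.i.d. and measures no drug concentrations (SAP 9.5.4), that table is the planned description of how long each regimen was taken. The rule hides the subjects who never reached the later regimens.

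**Working it through.** **Inputs.** Nominal visit days from the schedule of assessments: Visit 3 = Day 1, Visit 4 = Day 7, Visit 5 = Day 14, Visit 6 = Day 21. Let L be the day of the last dose and V3 to V6 the visit days. Group size is 20 (SAP 9.7.2).

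**The SAP rules as written.**
- Morning = (L if V3 ≤ L ≤ V4, otherwise V4) − V3 + 1
- Evening = (L if V4 + 1 ≤ L ≤ V5, otherwise V5) − V4
- B.i.d. = (L if V5 + 1 ≤ L ≤ V6, otherwise V6) − V5
- Total = L − V3 + 1, the first dose being given at Visit 3

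**The plan's own figure first.** For a completer, L = 21: morning 7 − 1 + 1 = 7, evening 14 − 7 = 7, b.i.d. 21 − 14 = 7. The sum is 21, and the total is 21 − 1 + 1 = 21. This reproduces the planned 7 + 7 + 7 days and shows that the three components partition total exposure when dosing is completed.

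**Subjects who stop but attend Visits 4 to 6.**

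| Last dose | Morning | Evening | B.i.d. | Sum | Total by SAP |
|---|---|---|---|---|---|
| Day 1 | 1 | 7 | 7 | 15 | 1 |
| Day 4 | 4 | 7 | 7 | 18 | 4 |
| Day 7 | 7 | 7 | 7 | 21 | 7 |
| Day 10 | 7 | 3 | 7 | 17 | 10 |
| Day 14 | 7 | 7 | 7 | 21 | 14 |
| Day 15 | 7 | 7 | 1 | 15 | 15 |

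The sum exceeds the total for every last-dose day from 1 to 14 and agrees from Day 15 on. For Days 1 to 6, one later regimen alone (7 days) exceeds total exposure.

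**Other schedules.** The same mismatch, for all last doses up to and including Visit 5, appears with visits on Days 1/9/16/23, 1/9/18/27 and 1/6/12/18. The last of these follows the visit spacing in Protocol 7.1.4 to 7.1.6 (5, 6 and 6 days). That spacing does not match the nominal days and needs reconciling separately; it does not change the result here.

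**Arm-level size.** The documents give no number of early stoppers, so this is an assumption with a range. Suppose k of 20 stop by Visit 4 and stay, and the rest complete. The SAP reports mean b.i.d. exposure as 20 × 7 / 20 = 7.00 days whatever k is. The true mean is (20 − k) × 7 / 20:
- k = 1: 133 / 20 = 6.65
- k = 2: 126 / 20 = 6.30
- k = 3: 119 / 20 = 5.95
- k = 4: 112 / 20 = 5.60

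Mean evening exposure behaves in the same way. With k = 0 there is no error.

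**Missing visit dates.** If a subject leaves between Visits 4 and 5, there is no Visit 5 date. The window test for evening dosing then has no upper bound, and the b.i.d. formula has no start. The evident intent is to close evening exposure at the last dose, but the SAP does not say so. This is an unstated convention, not a miscalculation.

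**The case against.** The strongest reply is that the consequence is small. SAP 9.7.1.6.1 bases adverse event percentages on the number of subjects in each treatment group. It plans no event summary by regimen and no rate per day of exposure, and per-regimen duration feeds no other analysis. Early stopping is also visible elsewhere: in total exposure, the disposition row for withdrawal from study drug with rescue, adverse events leading to drug discontinuation, adherence by visit, and the listings. A programmer might well assign zero b.i.d. days to someone with no b.i.d. dosing. All of this stands as a limit on the harm. It does not repair the rule, because the written text yields 7 days, not 0.

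The error is also conditional: it needs a subject who stops on or before Visit 5 and still has the later visit dates. Protocol 4.5 does not regard retention as a major issue. That is weak reassurance, however, because the error comes from subjects who are retained after stopping. A subject who leaves outright has a missing value, not an inflated one.

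A reader might infer two stronger things. One is that the b.i.d. safety conclusions rest on inflated exposure; the documents plan no such exposure-based statement. The other is that the error will differ between arms, for example through rescue on vehicle and intolerance on 0.04%. The documents give no rates for either. Both would inflate exposure in their own arm and could partly offset each other, so no direction can be claimed.

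**Conclusion.** The rule is wrong as written. It is a stated derivation that returns a wrong number for a type of subject the documents expect, and it can contradict the total-exposure formula in the same section (21 days against 7 for a last dose at Visit 4). It is not certain that any reported figure will be wrong: if nobody stops on or before Visit 5 and stays, the formulas are correct. With 1 to 4 such subjects per arm of 20, all stopping by Visit 4, mean b.i.d. exposure would be overstated by 0.35 to 1.40 days (7.00 − 6.65 and 7.00 − 5.60). The count is an assumption. The effect is confined to the descriptive per-regimen exposure summary. It is worth correcting because the correction is cheap, not because a main result depends on it.

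**What to change.** Replace the evening and b.i.d. rules in SAP 9.7.1.4 with:

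- Evening = max(0, min(last dose, Visit 5) − Visit 4)
- B.i.d. = max(0, min(last dose, Visit 6) − Visit 5)

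Then state what happens when a visit date is missing:

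- If the subject left the study without the Visit 4, 5 or 6 date and has no later visit, close the current regimen at the last-dose date and set later regimens to 0. For example, last dose Day 10 and no Visit 5 gives 7 + 3 + 0 = 10.
- If an intermediate visit was missed but dosing continued, use the recorded date of the regimen switch, not the last-dose date. Otherwise a subject who missed Visit 5 and dosed to Day 21 would be given 21 − 7 = 14 evening days, absorbing any b.i.d. days. The documents do not say that a switch date is captured, so the study drug administration eCRF should be checked for it.

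Add a programmed check that the three components sum to total exposure for every subject. With all visit dates present, the revised formulas, taken with the existing morning rule, satisfy this for every last-dose day in all four schedules tested. For example, last dose Day 7 gives 7 + 0 + 0 = 7. Completers are unchanged at 7 + 7 + 7 = 21.

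The cost is a few lines of SAP text and derivation code. No new data are needed, provided the switch date is already recorded for anyone who missed an intermediate visit.
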